### Urine

Collect urine in a sterile container (5 mL each). Label the tube with the Subject's Study ID number, study visit, date of visit, and "urine". **Do not write the subject's name or any other**

**identifying information on the urine tube.** Place the tube upright in a rack in the refrigerator (2 to 8°C).

If need to transport to the lab for storage prior to shipping, wrap the tube in a paper towel and place it in a plastic bag with an absorbent pad. Place the plastic bag containing the tube in Styrofoam mailer with a frozen gel pack or on ice. The gel pack will ensure refrigerator temperature (2 to 8°C) during transport to the laboratory.

### **Whole Blood**

#### *Ex vivo assays:*

**Collect 1 purple-top (EDTA) tube (10 mL).** Label the tube with the Subject's Study ID number, study visit, date of visit, and "whole blood". **Do not write the subject's name or any other identifying information on the blood tube.** Send to [name] per instructions below for arrival at [name] lab within 36 hours of sample collection.

#### *Genetic Testing*

**Collect 1 purple-top (EDTA) tube (5 mL).** Label the tube with the Subject's Study ID number, study visit, date of visit, and "whole blood". **Do not write the subject's name or any other identifying information on the blood tube.** Send to [name]/[name] per instructions below.

#### *Immunologic phenotyping*

**Collect 1 purple-top (EDTA) tube (5 mL).** Label the tube with the Subject's Study ID number, study visit, date of visit, and "whole blood". **Do not write the subject's name or any other identifying information on the blood tube.** Send to [name]/[name] per instructions below.

#### *RNA expression*

**Collect 1 PAXgene RNA tube (2.5 ml blood in a 10 ml tube).** Invert 8-10 times immediately after drawing. Maintain tubes in upright position at room temperature for a minimum of 2 hours. Store PAXgene tubes in a wireframe rack (Styrofoam racks may cause the tubes to crack). Transport to TGPS laboratory on ice.

**\*\*\*For EDTA (1) and PAXgene RNA tube (1)** please email the following people the day prior to a subject's scheduled visit to expect samples from the visit: [name], [[contact]](mailto:[contact]), [name], [[contact]](mailto:[contact]), [name] [[contact]](mailto:[contact]), and [name], [[contact]](mailto:[contact]).

All specimens must be labeled with a code. Unlabeled specimens will be destroyed.

All specimens must be accompanied by a completed lab sheet.

### 6.2.3 Specimen Shipment

*Whole blood for immunologic phenotyping, genetic testing, and ex vivo assays by [name] collected at Harbor-UCLA* will be shipped at ambient temperature by Fed Express overnight, following International Air Transport Association (IATA) regulations (double package or bag all specimens; include an absorbent square in each bag; affix "Exempt Human Specimens" label to box). Ship for arrival within 36 hours of collection to:

[name]/[name]  
[name]  
[name]  
Minneapolis, MN [contact]

Contact [name] 48 hours in advance by Phone (above) or Email: [[contact]](mailto:[contact]) prior to shipping. Deliver before 10:30 am on Tuesday – Thursday.

Contact [name] by [contact] or email: [[contact]](mailto:[contact]) 48 hours prior to shipping.

### ***Bone Biomarkers***

Samples for bone biomarkers will be stored at each site at -80°C until the end of the study at which time all samples will be shipped/transported on an adequate amount of dry ice to [name], Cytokine Reference Lab. For shipping samples to [name], samples will be shipped on an adequate amount of dry ice to the study PI following International Air Transport Association (IATA) regulations (double package or bag all specimens; include an absorbent square in each bag; affix "Exempt Human Specimens" label to box). Ship for arrival within 36 hours:

[name]

Cytokine lab  
[name]  
[name]  
[name]

Contact [name] 48 hours in advance by [contact] or email: [[contact]](mailto:[contact]). Deliver before 10:30 on Tuesday – Thursday.

### ***Storage***

Samples for storage will be kept at each study site at -80°C until the end of the study at which time all samples will be shipped on an adequate amount of dry ice to the study PI following International Air Transport Association (IATA) regulations (double package or bag all specimens; include an absorbent square in each bag; affix "Exempt Human Specimens" label to box). Ship for arrival within 36 hours:

[name]  
[name]  
[name]  
[name]

Contact [name] 48 hours in advance by [contact] or email: [[contact]](mailto:[contact]) prior to shipping. Deliver before 10:30 on Tuesday – Thursday.

#### **6.2.4 Serum Sample Procedure for Immunogenicity assays:**

Collect blood samples to analyze Anti-Drug Antibodies (ADA) to IFN- $\gamma$  and Neutralizing antibodies (Nab) to IFN- $\gamma$  levels using 4.0 mL blood collection tube tubes (BD Vacutainer® SST™ Serum Separation Tubes).

Collect a minimum of 2mL serum per time point described in Table 1.

After obtaining the blood sample, inverting the collection tube 5 times allow the blood to clot for 30 minutes at ambient temperature (19-24°C).

Centrifuge sample at approximately 1000-1300 RCF for 10 minutes at room temperature in a swinging bucket centrifuge.

Transfer duplicate serum aliquots of approximately equal volume (minimum of 2 x 100  $\mu$ L for ADA and 500  $\mu$ L for Nab with backup of 500  $\mu$ L per aliquot), using standard laboratory technique, into 2 polypropylene cryovials.

Secure a label to each storage tube. Labels should contain the following information:  
Sponsor: [name]

Sample Type: Human serum  
Sample date: DD-MMM-YYYY  
Sample time: XX:XX  
Protocol: 21549-01  
Subject Number: TBD  
Time point: TBD  
Serum Aliquot: TBD

Within 90 minutes of collection, store both aliquot samples upright at -20°C +/-5°C or -70°C ± 10°C.

Store at -70°C ± 10°C until collection of month 12 sample, then ship all study subject samples as follows. If samples are collected after month 12, then ship immediately to Intertek as follows.

Ship as separate shipments Serum Aliquot 1 and Serum Aliquot 2 samples for potential analysis of ADA and Nab with an adequate supply of dry ice via Fedex Monday through Wednesday to:

Attn: [name] (ADA samples) or [name] (Nab samples)  
Intertek Pharmaceutical Services  
[name]  
[name]

Provide an inventory log listing of all samples shipped with each shipment. Include a paper copy with the shipment and an electronic version via email to [name] ([[contact]](mailto:[contact])) and [name] ([[contact]](mailto:[contact])).

Send a shipment notification including a confirmation of the shipment date, courier name, and tracking information via email to [name] ([[contact]](mailto:[contact])) and [name] ([[contact]](mailto:[contact])).

## 6.3 Clinical Procedures

### 6.3.1 Medical History

A study physician and/or study coordinator will review the following with the subject/parent or legal guardian at the screening baseline visit:

- Current and past 1 year prescription medications and doses,
- current and past medical history,
- review of systems,
- family history,
- number of hospitalizations over the last 12 months, and

- number of days treated with antibiotics over the last 12 months.

For patients <18 years of age, height data will be collected from 6 and/or 12 months prior to the baseline visit.

Changes in the medical history and a complete review of systems will be reviewed at each subsequent visit.

If a subject is unable to return to the clinical site for the Month 3 visit they will be contacted via telephone to discuss any changes in health since their last study visit and then withdrawn from the study. Three attempts will be made to contact the subject by phone before terminating the patient on the study.

### 6.3.2 Laboratory Evaluations

Blood and urine will be collected at the time points described in Table 1.

CBCD, LFT, ESR, 25OHD, Calcium, iPTH, UA, urine ca:cr will be performed in real time by the Fairview Diagnostics Laboratory at UMN and at Quest for subjects seen at Harbor-UCLA at baseline, 3, 6, and 12 months. BMP, LFT, and UA will be performed at UMN, Quest, or the subject's local clinical lab at weeks 4 and 6, and month 9. Anti-drug antibody testing will be performed by Intertek Pharmaceutical Services at Baseline, at weeks 3 and 6, and months 3, 6 and 12, after the first dose, and 2-3 weeks after last dose, and then every 4-6 weeks until values return to baseline. Genetic testing for mutations in TCIRG1, CLCN7, CAII, OSTM1 and RANKL genes will be performed at the Baseline visit at the University of Minnesota for patients who have not had an osteopetrosis related mutation previously identified.

25OHD will be measured by liquid chromatography tandem mass spectrometry, and an attempt will be made to maintain levels between 30 ng/ml and 75 ng/ml. Treatment of vitamin D insufficiency/deficiency will be as follows:

#### Vitamin D insufficiency: total 25-OH vitamin D 20-29 ng/ml

Age	Vitamin D	Calcium (elemental)*
0-1 years	1,000 IU/d x 8 weeks	NA
1-3 years	1,000 IU/d x 8 weeks	500 mg/d
4-8 years	1,000 IU/d x 8 weeks	800 mg/d
>8 years	2,000 IU/d x 8 weeks	1,300 mg/d

\*Add calcium supplements if oral intake is inadequate or serum calcium is low.

#### Vitamin D deficiency: total 25-OH vitamin D 10-20 ng/ml: obtain PTH and serum calcium levels.

Age	Vitamin D	Adequate Intake Calcium (elemental)*	If PTH>65 pg/ml or serum calcium is low, add additional calcium as follows: Calcium (elemental) max dose 2000 mg/day Start at higher dose and taper over 4 weeks to AI.
0-1 years	2,000 IU/d x 8 weeks	NA	30-75 mg/kg/day divided 2-4 times daily
1-3 years	2,000 IU/d x 8 weeks	500 mg/d	30-75 mg/kg/day divided 2-4 times daily
4-8 years	4,000 IU/d x 8 weeks	800 mg/d	30-75 mg/kg/day divided 2-4 times daily
>8 years	50,000 IU/wk x 8 weeks (Rx)	1,300 mg/d	30-75 mg/kg/day divided 2-4 times daily

\*Ensure oral intake of calcium is adequate.

**Severe Vitamin D deficiency: total 25-OH vitamin D <10 ng/ml: obtain PTH and serum calcium levels.**

Age	Vitamin D	For all patients with severe vitamin D deficiency: Calcium (elemental) max dose 2000 mg/day Start at higher dose and taper over 4 weeks to AI.
0-1 years	2,000 IU/d x 8 weeks	30-75 mg/kg/day divided 2-4 times daily
1-3 years	2,000 IU/d x 8 weeks	30-75 mg/kg/day divided 2-4 times daily
4-8 years	4,000 IU/d x 8 weeks	30-75 mg/kg/day divided 2-4 times daily
>8 years	50,000 IU/wk x 8 weeks (Rx)	30-75 mg/kg/day divided 2-4 times daily

For post-menarchal female patients, a urine pregnancy test will be performed at Screening and before the Baseline, Month 3, and Month 6 visits. Plasma and serum will be collected as described in Table 1. Immunologic phenotyping will be performed by University of Minnesota. BAP, P1NP, OPG, CTX, TRAP5b, RANKL, and CK-BB will be performed by the Fairview Cytokine Reference Laboratory at the University of Minnesota. Expression, methylation, and genotype data will be generated at LABioMed in the laboratories of Drs. [name] and [name].

### 6.3.3 Medical examination and Anthropometrics

A trained pediatric provider will perform a physical examination at each visit. Tanner staging of pubertal development, including breast and pubic hair development in girls, and testicular size and pubic hair development in boys will be performed at baseline, 6, and 12 months for participants < 18 years of age or < Tanner stage 5. Height will be measured 3 times standing without shoes. The average of 3 measurements by the same observer using identical technique with a wall-mounted stadiometer will be recorded. Each subject will be repositioned between each measurement. Height standard deviation score (SDS) will be calculated based on the

National Center for Health Statistics 2000 data as provided by the Center for Disease Control. Weight to be measured standing, once with subject in light clothing or dressing gown with shoes removed. These measurements will be used to calculate body mass index (BMI) as weight (kg) divided by height ( $m^2$ ).

#### **6.3.4 Radiographic assessments**

##### **6.3.4.1 Dual energy x-ray absorptiometry (DXA)**

DXA (Hologic [Harbor] and GE [Minnesota]) measurements will be obtained for total body less head, L1-L4 lumbar spine, and for subjects  $\geq 18$  years of age femoral neck and total hip as well. Standardized procedures for participant positioning and data processing will be used for all scans. Standardization of data from different machines is done by standardized phantom scanning protocols.

##### **6.3.4.2 Peripheral quantitative computed tomography (pQCT)**

Detailed measures of bone mass and strength will be assessed using pQCT (XCT 2000L [Harbor-UCLA] and XCT-3000 [UMN], Orthometrix Inc., White Plains, NY). This is a non-invasive technique that allows for 3-dimensional assessment of bone volumetric density, bone geometry and estimates of bone strength. Images will be taken at the 3%, 38%, and 66% sites of the left tibia and the 3% and 38% sites of the non-dominant radius. The reference line will be the proximal end of the distal growth plate. Standardized procedures for participant positioning and data analysis will be used for all scans. Image processing and calculation of bone parameters will be completed using the manufacturer's software (version 5.5) and thresholds established in the literature.

#### **6.3.5 Pain and physical function testing**

##### **6.3.5.1 Child Health Questionnaire - Parent Form 50 (CHQ-PF50)**

The CHQ-PF50 is a 50-item, parent-completed questionnaire designed to measure the physical and psychosocial well-being of children between the ages of 5 and 18. The CHQ-PF50 has been widely used in studies of chronic illness in childhood. Twelve components of quality of life are measured including: physical functioning, role/social limitations due to physical health, bodily pain/discomfort, general health, mental health, role/social limitations due to emotional-behavioral difficulty, behavior, and self-esteem. The impact of the child's disorder on parents and family functioning (i.e., time impact, emotional impact, family activities, family cohesion) are also measured. Items are measured on a likert scale, summed for each subscale and linearly transformed to a 0 to 100 scale, where higher scores reflect better functioning. Composite scores for physical functioning (Physical Summary Score) and psychosocial functioning (Psychosocial Summary Score) are calculated based on population norms. This questionnaire will be administered to all participants between the ages of 5 and 17 years.

### **6.3.5.2 Medical Outcomes Study Short Form-36 (SF-36)**

The SF-36 is a widely used measure of patient-reported quality of life for participants 18 years of age and older. The SF-36 measures 8 health domains, including physical functioning, role limitations due to physical health, bodily pain, general health perceptions, vitality, role limitations due to emotional problems, and mental health. Items are rated on a Likert scale. Summed scores of the scales are then transformed linearly to values from 0 (worst health) to 100 (best health). Two summary measures (Physical and Mental Component Summary scores) are derived from population-based normative data. The SF-36 has been used in studies of adult chronic illness, and as an important component of treatment outcome studies. This questionnaire will be administered to all participants aged 18 years and above.

### **6.3.5.3 Patient and parent-reported pain intensity (acute and within the past week).**

Visual analogue scales from the Pediatric Pain Questionnaire (PPQ) (22) will be used to assess intensity of the child's pain from the child's and parent's perspective (for children ages 5-17). Visual analogue scales are widely used in both pediatric and adult pain studies due to their good reliability and validity, and they do not tend to result in the clustering of scores as can be seen with Likert-type scales (23,24). The visual analogue scales included in the PPQ consist of two 100 mm horizontal lines that measure both present pain and pain in the past week. Each line is anchored with developmentally appropriate pain descriptions (i.e., "No pain, Not hurting" to "Hurting a whole lot, Severe pain") and accompanying happy and sad faces. Scores on the PPQ range from 0 to 100, with higher scores representing more pain. For adults, the Visual Analogue Scale (VAS) for Pain (25,26), a 100 mm horizontal line with anchors appropriate for adults, ranging from "no pain" to "pain as bad as it could be; worst possible pain," will be used to assess pain intensity in the present moment and over the past week. As in the PPQ visual analogue scales, the VAS score is determined by measuring the distance (mm) on the 100 mm horizontal line between "no pain" and the patient's mark, providing a range of scores from 0-100, with higher scores representing more pain intensity.

For participants aged 18 years and older, pain intensity and its impact on daily functioning will be captured as part of the SF-36 questionnaire.

### **6.3.5.4 Infectious Outcomes**

The frequency of infectious outcomes will be quantified by asking participants for the number of hospitalizations in the last 3 months and the number of days treated with antibiotics over the last 3 months (IV and PO will be counted separately). The type of infectious organism will be documented as well.

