### 4.2 Secondary Hypotheses

The secondary hypotheses are:

1. Compared to baseline, treatment with IFN- $\gamma$ 1b will result in:
  - a. Decreased tibial volumetric bone mineral density (**vBMD**) and estimated bone strength measured by peripheral quantitative computed tomography (**pQCT**);
  - b. Decreased total body and lumbar spine areal BMD (**aBMD**) by dual-energy x-ray absorptiometry (**DXA**);
  - c. Increased levels of markers of bone remodeling (see Table 1);
  - d. Increased osteoclast activity by *in vitro* testing;
  - e. Increased white blood cell (**WBC**) and platelet counts in patients that have lower than expected blood counts at baseline.
  - f. Increased height standard deviation score (**SDS**) for participants <18 years with open growth plates;
  - g. Decreased inflammation measured by erythrocyte sedimentation rate (**ESR**);

[figure not shown]
- h. Decreased pain score (based on prior 4 weeks);
  - i. Increased physical function score (based on prior 4 weeks); and
2. Compared to the 12 months prior to study entry (based on medical record review or subject recollection), treatment with IFN- $\gamma$ 1b over 12 months will result in:
  - a. Decreased number of hospitalizations for infection;
  - b. Decreased number of days treated with antibiotics;
  - c. Beneficial change in WBC and platelet counts in patients who have lower than expected blood counts at baseline;
  - d. Beneficial change in ESR;
  - e. Increased height SDS for participants  $<18$  years with open growth plates; and
3. Patients will not develop neutralizing antibodies.

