## 5 Study Design

### 5.1 Overview of Study Design

This is a multi-center, open-label, 12-month clinical trial of ACTIMMUNE treatment of patients with intermediate osteopetrosis. Study design is summarized in Figure 1. Routine clinical safety and efficacy data (see Table 1) will be obtained at baseline, weeks 4 and 6, and months 3, 6, 9, and 12

following the initiation of therapy. Additional outcomes (see Table 1) will be obtained at baseline, 3, 6 and 12 months.

\*Includes medical history, ECHO, and EKG.

Fig. 1. Study Design Schematic

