## 5.3 Evaluations and study timeline

Table 1. Evaluations and study timeline

	Screening a	Baseline	# of months from 1 st IFN- $\gamma$ 1b treatment ( $\pm$ 1 week)		
			3	6	12
General					
• Medical history	X	X	X	X	X
• Physical exam		X	X	X	X
• Genotype b		X			
• Anthropometric measurements	X	X f	X	X	X
• RNA and DNA assays		X	X	X	X
Safety Measuresc					
• Basic metabolic panel (BMP)	X	X	X	X	X
• Liver function tests (LFT)	X	X	X	X	X
• Urine pregnancy test (UPT) e	X	X	X	X	X
• Urinalysis (UA)	X	X	X	X	X
• ECHO with interpretation	X				
• EKG with interpretation	X				

• Anti-drug antibodies (ADA) g		X	X	X	X
Bone Biomarker Testingd					
• Formation Testing (bone specific alkaline phosphatase [BAP], type 1 procollagen [P1NP])	-	X	X	X	X
• Resorption testing (C-telopeptide [CTX], Tartrate resistant acid phosphatase type5b [TRAP5b])	-	X	X	X	X
• RANKL, OPG, CK-BB	-	X	X	X	X
Endocrine Assessment					
• Total 25-OH Vitamin D (25OHD) h	-	X	X	X	X
• Serum ionized calcium	-	X	X	X	X
• Urine calcium: creatinine	-	X	X	X	X
• Intact parathyroid hormone (iPTH)	-	X	X	X	X
Inflammatory/Immunology					
• CBC with differential and platelets	-	X f	X	X	X
• Erythrocyte sedimentation rate (ESR)	-	X f	X	X	X
• Immunologic phenotyping (CD3, 4, 8, 14, 15, 16, 19, 34, 56)	-	X	X	X	X
Neuropsychological testing					
• Pain assessment	-	X	X	X	X
• Quality of life survey	-	X	X	X	X
Orthopedic assessment					
• Dual energy X-ray absorptiometry (DXA) lumbar spine, total body, total hip and femoral neck (adults $\geq 18$ yrs only)	-	X	-	-	X
• Peripheral Quantitative CT (pQCT) left tibia	-	X	-	X	X
In vitro osteoclast function assays – [name] Lab					
• Gene expression – osteoclast marker genes	-	X	X	X	X
• Osteoclast activity – ability to release calcium phos from coated plate	-	X	X	X	X
Infectious outcomes					
• Number of hospitalizations in prior 3 months	-	X f	X	X	X
• Number of days treated with antibiotics in last 3 months	-	X f	X	X	X
• Type of infectious organism	-	X f	X	X	X
RANKL=Receptor activator of nuclear factor kappa-B ligand; OPG=osteoprotegerin; CK-BB=creatinine kinase isoenzyme BB.					
a Screening visit evaluations will count for baseline evaluations where applicable. Screening visit will be within 3 months of baseline visit					

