b Genetic testing for CLCN7, CAII, TCIRG1, OSTM1, and RANKL mutations will be done at the University of Minnesota if not already performed clinically					
c Safety labs will also be obtained at weeks 4 and $6 \pm 2$ days, and month $9 \pm 1$ week; subjects will be contacted on a weekly basis either by email or telephone to monitor safety during the initial 4 week dose escalation period.					
d Sample collection will be postponed if needed to ensure collection is more than 2 weeks since last fever ( $>100.4^{\circ}\text{F}$ [ $38^{\circ}\text{C}$ ] axillary) or fracture.					
e Post-menarchal females.					
f Height (for subjects $<18$ years), CBC, and ESR will be obtain from the patient's medical record when available and number of hospitalizations and infectious data from the patient's medical record or if not available then the patient's recollection at the baseline visit.					
g ADA testing will also be performed at weeks 3 and $6 \pm 2$ days after the first dose, and 2-3 weeks after last dose, and then every 4-6 weeks until values return to baseline.					
h 25OHD level will be checked at 6 weeks as well.					

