#### *Serious Adverse Event (SAE)*

An SAE is any AE that is:

- Fatal

- Life-threatening
- Requires or prolongs a hospital stay
- Results in persistent or significant disability or incapacity
- A congenital anomaly or birth defect

Important medical events are events that may not be immediately life-threatening, but are clearly of major clinical significance and may be SAEs. They may jeopardize the subject, and may require intervention to prevent one or the other serious outcomes noted above.

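### Infection data for the year before entry come from medical records first, but on-treatment counts come from asking participants with no stated record check, so hypotheses 2a and 2b compare unequally ascertained periods

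*Combined protocol and SAP*

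**What the plan says.** **The comparison.** Section 4.2, hypothesis 2, sets the comparator: "Compared to the 12 months prior to study entry (based on medical record review or subject recollection"). Items 2a and 2b predict fewer hospitalizations for infection and fewer antibiotic days over 12 months of treatment. Section 5.1 describes an open-label trial, and the Study Summary gives a single arm.

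**Before treatment.** Footnote f to Table 1 (Section 5.3), repeated in Appendix B, takes "number of hospitalizations and infectious data from the patient's medical record or if not available then the patient's recollection at the baseline visit". In both schedules the marker for this footnote stands on the three infection rows in the Baseline column only. Section 4.2 allows either source without an order. Section 6.3.1 also has staff go through the prior year with the subject or parent, including "number of hospitalizations over the last 12 months, and" days on antibiotics.

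**On treatment.** Section 6.3.5.4 defines the measurement: "The frequency of infectious outcomes will be quantified by asking participants for the number of hospitalizations in the last 3 months". The same sentence covers days on antibiotics, with IV and oral counted separately. It mentions no record review. Section 5.1 sets the times: "Additional outcomes (see Table 1) will be obtained at baseline, 3, 6 and 12 months".

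**A parallel route for admissions.** Section 8.1 makes an adverse event serious if it "Requires or prolongs a hospital stay". Section 8.3.1 requires an SAE report within 24 hours and a written narrative within the following 48 hours. No section says that these reports feed or check the infection endpoint.

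**The concern.** In a before-after comparison within subjects, the same ruler has to be used twice. Here the prior year is read from records where they exist, and the treated year is read from what the participant or parent remembers. If the two methods capture different shares of the true events, the difference enters the estimated change directly, and no control arm is present to cancel it.

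The imbalance is plausible in practice. Section 5.4.3 has medical records reviewed to confirm eligibility, and a serious infection in the prior year is one of the qualifying criteria in Section 5.4.5, so prior infections are likely to be documented. Section 5.4.3 also expects subjects to travel long distances, and Section 6.4 allows unscheduled visits with local physicians. Care during treatment may therefore take place elsewhere, and the endpoint text does not ask for those records.

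Section 2.3 says that encouraging data will be used to raise clinicians' awareness of the treatment, and Section 7.2.1 says that the pilot feeds a definitive trial. An apparent fall in antibiotic days would be used for both.

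**Working it through.** The plan states no infection rate, recall accuracy, effect size or power, so there is no figure of its own to reproduce. What follows is algebra on assumed capture values.

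**Inputs**
- *s*: share of true on-treatment events captured by asking. Assumed 0.90, 0.80, 0.70.
- *r*: share of true prior-year events captured by records. Assumed 1.0 or 0.9.
- *q*: share of true prior-year events captured by 12-month recollection. Assumed 0.6 or 0.8.
- *f*: share of the baseline counts that rest on recollection. Unknown; taken as 0, 0.5 and 1.
- True drug effect: zero. All 12 treatment months are taken as covered, to isolate the effect of source.

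**Formula**

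Baseline capture B = (1 − f) × r + f × q

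Apparent fall = 1 − s / B (a negative value is an apparent rise)

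**Complete baseline records** (f = 0, r = 1, so B = 1): 1 − 0.90 = 10%; 1 − 0.80 = 20%; 1 − 0.70 = 30%. For example, 100 true antibiotic days in each year would be counted as 100 before and 80 during treatment at s = 0.80.

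**Other mixes of baseline source**

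| Baseline | B | s = 0.90 | s = 0.80 | s = 0.70 |
|---|---|---|---|---|
| All records, r = 1 | 1.00 | 10% | 20% | 30% |
| All records, r = 0.9 | 0.90 | 0% | 11.1% | 22.2% |
| Half records (r = 1), half recall (q = 0.8) | 0.90 | 0% | 11.1% | 22.2% |
| Half records (r = 1), half recall (q = 0.6) | 0.80 | −12.5% | 0% | 12.5% |
| All recall, q = 0.8 | 0.80 | −12.5% | 0% | 12.5% |
| All recall, q = 0.6 | 0.60 | −50% | −33.3% | −16.7% |

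The sign depends on whether s is below or above B. With r = 1, q = 0.6 and s = 0.80, the bias favors the drug when fewer than half of the baseline counts are recalled, vanishes at half, and runs against the drug beyond that.

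**Same source and equal capture in both periods:** s = B, so the apparent fall is 0%.

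**Second source on treatment, by endpoint**
- Hospitalizations (2a): SAE reports exist for admissions due to an adverse event. They are not linked to the endpoint, and Section 8.2 has adverse events sought mainly by questioning at each contact.
- Antibiotic days (2b): no second source is named.

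The assumption of full coverage is for isolation only. Three 3-month look-backs at months 3, 6 and 12 cover 9 of 12 months. That is a separate matter, which a common source order would not by itself repair.

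**The case against.** The strongest reply is that the trial is unlikely to miss an admission. Intercurrent illnesses are adverse events, admissions for them are SAEs, changes in medical history are reviewed at every visit (Section 6.3.1), adherence is queried monthly (Section 6.5), and hospital records are listed among source documents (Section 9.2). Organism type is also collected at months 3, 6 and 12, and recall alone would seldom supply it. This stands in part: a reader might infer that on-treatment information comes only from asking, and for hospitalizations the documents do not support that. But Section 9.2 is a general definition, nothing directs staff to request records for this endpoint, and none of these routes is stated to capture days on antibiotics.

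A second reply concerns direction. A reader might infer that any recall loss on treatment shows up as a drug benefit. That holds only for on-treatment loss taken alone. Baseline may rest on a 12-month recollection, which is a longer look-back than the 3 months used on treatment, and records may be incomplete. Either can cancel or reverse the bias, as the table shows. This reply stands in full.

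Third, a reader might want a false-positive rate. The documents do not support one: they give no event rate or dispersion, and Section 7.2.2 does not name hospitalizations or antibiotic days among the endpoints for paired testing.

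Lastly, these are secondary outcomes in a 10-subject pilot whose primary endpoint is feasibility and tolerability. That limits the weight of the point but does not remove it.

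**Conclusion.** The point holds in this form: the stated measurement rules put records first before treatment and name only participant report during it, so 2a and 2b are unequally ascertained in an uncontrolled comparison. It bears mainly on antibiotic days and less on hospitalizations.

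If baseline records are complete and on-treatment capture is 90%, 80% or 70%, a drug with no effect shows a fall of 10%, 20% or 30%. Those capture values are assumptions; the documents give none. If baseline rests partly or wholly on 12-month recall, the bias shrinks or reverses: at an assumed 60% baseline capture and 80% on treatment, it becomes an apparent rise of about 33%. The net sign cannot be settled from the documents, because it depends on how many subjects have usable records and how complete those are. The plan does not require the source of each count to be recorded, so a reader of the results could not settle it either.

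**What to change.** 1. In Section 6.3.5.4 and in footnote f (Table 1 and Appendix B), apply one source order at baseline and at months 3, 6 and 12: medical records first, recollection only where no record exists. Align Section 4.2, which now gives no order.
2. Reconcile on-treatment admissions with the SAE forms before the infection data are analyzed.
3. Add a CRF field for the source of each count (record, recollection or both).
4. Report 2a and 2b in all subjects, with a sensitivity display by source in each period. Do not make subjects with matching sources the main analysis: that would subset 10 subjects on record availability, and it would still pair 12-month with 3-month recall.

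The cost is a short protocol change, one CRF field, and record requests for up to 10 subjects. The requests are the real burden, since subjects may receive care far from the study centers and some records will not arrive. Treatment and visits are unchanged.
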